The incidence of spasticity is reported to be 20%-40% in post-stroke survivors. It not only has downstream effects on the patients' quality of life, also lays substantial burden on the caregivers and the society. Botulinum neurotoxin (BTX) is considered as the first-line treatment for focal spasticity management. Intramuscular BTX injection has proven to be a relatively safe procedure (Bakheit 2006), but it may still cause side effects or even severe problems in patients such as blocking of autonomic nerves, muscle atrophy by anatomical denervation and immunological reactions (Klein 2002; Dressler and Hallett 2006; Warner et al. 2006; Simpson et al. 2008). The occurrence and severity of side effects are dependent on the delivered dose of toxin (Borodic et al. 1990; Eleopra et al. 1996), and it has been clinically shown that injection of a minimum effective dose reduces the presence of adverse effects (Brans et al. 1995). BTX acts on the neuromuscular junction (NMJ) and the effectiveness of the BTX injection depends on the proximity of the injection site to the NMJ (Jahn 2006). Studies have demonstrated that increasing the injection distance by 1cm from the NMJ indicated by the innervation zone (IZ) of muscles reduced the effect of BTX by 46% (Lapatki et al. 2011). Furthermore, IZ locations vary between muscles and individuals (Guzmán-Venegas et al. 2014). Therefore, it is critical to accurately identify the 3-dimensional (3D) IZ distributions in the spastic muscles for specific patients to guide BTX injections for the best clinical effect with the minimum dose.

Significant efforts have been taken to localize IZ locations from skin surfaces from multi-channel surface EMG recordings (Merletti et al. 2004; Barbero et al. 2011; Beretta Piccoli et al. 2014; Boccia and Rainoldi 2014; Guzmán-Venegas et al. 2014), however, there is no technique currently available for defining IZ distributions in 3D space of spastic muscles to guide BTX injections in specific patients. The minimal amplitude channel and/or the channel with phase reversal in the single differential signal have been utilized to identify the surface IZ locations (Merletti et al. 1999). The IZs can be localized over the skin

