Composite surface EMG signals can be decomposed into their constituent MUAP trains (Ning et al. 2015). We recently developed a novel 3-dimensional innervation zone imaging approach (3DIZI) by combining the muscle activity imaging and surface EMG decomposition methods to image the distribution of IZs in the 3D space of the biceps from high-density surface EMG recordings (Liu et al. 2015). The surface location of the IZ of each decomposed motor unit (MU) was identified from the bipolar high-density MUAP trains, and was utilize to constrain the muscle activity imaging solution in the 3DIZI to improve its localization accuracy. Subsequently the 3DIZI can be used to accurately localize the IZs in the 3D space of target muscles. The 3DIZI has been validated in healthy the biceps in 2 male subjects, but has not been validated and applied to spastic muscles. In our recent study using surface linear-array EMG recordings (In Revision), we found IZ locations were asymmetrical between impaired and non-impaired biceps and large variations in IZ locations on the impaired side as well. The goal of this proposal is to validate the 3DIZI in spastic muscles, and to evaluate the feasibility of utilizing the 3DIZI to guide BTX injections in treating patients with muscle spasticity.

Innovation of this project

1) This research represents the first effort to image the 3D distributions of innervation zones in both healthy and spastic muscles. It provides ample opportunities for future basic research and clinical applications, such as the proposed application for guiding BTX injections.

2) This research will lead to a 3DIZ-guided BTX injection protocol which is innovative and clinically significant. Because BTX is injected to where its needs using this technique, the technique is able or expected to significantly reduce the dose, thus the cost of this very expensive treatment with improved clinical outcomes. Moreover, it is also expected to minimize possible adverse effects.

Preliminary results

In a pilot study (Liu et al. 2015), the 3DIZI was developed and evaluated with both simulated data and simultaneously recorded surface EMG and intramuscular EMG recordings from the biceps of 2 healthy subjects.

Development of the 3DIZI

Experimental setup and EMG recordings:

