The purpose of this Aim is to evaluate the feasibility of utilizing the 3DIZI technique to optimize BTX injections in patients with focal spasticity. Clinical and quantitative assessments of spastic biceps of stroke subjects between 3DIZI-guided and standard injections at baseline, 3 weeks, and 3 months post-injections will be compared. The clinical effect of BTX injection usually reaches to its peak at about 3 weeks, and lasts for 3 months. It is expected that outcomes (clinical and quantitative measures) will be better in the 3DIZI-guided injection group than in the standard injection group at 3 weeks and 3 months post-injection. Both groups are expected to have comparable baseline measures.

Patient selection: We plan to recruit 16 post-stroke subjects who are currently receiving BTX injections for their spastic biceps every 3 months at TIRR Outpatient Spasticity Management Clinic into two groups: the IZ-guided injection group and the standard injection group (Please see human subject protect section for characteristics of stroke patients).

BTX injections: Both groups of patients will be recruited prior to their routine BTX injection schedule. Baseline assessment (screening, clinical assessment, and quantitative assessment) will be performed 1 day prior to injection. Stroke patients with elbow flexors spasticity of modified Ashworth scale (MAS) of 2 or 3 will be recruited. The number of MAS (2s or 3s) will be matched between two groups. The type of BTX (we will choose botox because it is most commonly used in US) and amount of BTX (usually 100 units) and dilutions (usually double dilution) will be consistent between two groups. These parameters (type, dose, dilution) are standard of care at TIRR Spasticity Management Clinic. For standard injection procedures, target muscles will be visualized under ultrasound imaging which is operated by an experienced and dedicated technician. Position of needle tip within the target muscle is visualized prior to

[figure not shown]

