injection. Ultrasound guidance can help ensure depth of needle tip location, i.e., to make sure the needle tip is within the muscle, but it is not able to tell where it is located with reference to the IZs of the entire muscle. However, in the IZ-guided injection technique, IZ location obtained using the 3DIZ will be first marked over the skin surface of the muscle and the depth of the IZ will be also provided. The 3DIZ as described in Aim 1 will be applied to the IZ-guided injection group 1 day prior to scheduled injection. The surface location and depth information of the IZ will be used to guide where the needle tip needs to go. Currently, patients commonly receive 1 to 2 injection sites, occasionally 3 sites for biceps muscles. To standardize the procedure, we will choose 2 sites for all patients.

Treatment outcome evaluation and comparison: Treatment outcomes include clinical assessment of spasticity (MAS scale, see Human Subject Protection section) and quantitative assessment. Standard physical therapy will be ordered to both groups as part of standard of care for patients after BTX injections to maximize the outcomes. For quantitative assessment, we will adopt the same protocol in our recent study which quantified elbow flexors spasticity by measuring reflex torque (Figure 6)(Bhadane et al. 2015).

Fig. 6: Experimental setting (upper) and representative data (lower).

Each subject will receive a total of 60 degrees of computer-controlled elbow extension stretching at different speeds. The stretch ends at 10 degrees beyond the resting angle of the elbow joint during standing to offset the baseline difference among subjects (Bhadane et al. 2015). From the angle-torque relations, reflex torque is obtained after subtracting passive torque at 5°/sec from those at 50°/sec or 100°/sec. reflex torque is considered to reflect neural component of muscle spasticity (Kamper et al. 2001; Kamper et al. 2003; Li et al. 2006). It is expected to be reduced with spasticity reduction after neuromuscular blockade by Botox.

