There are very few risks associated with the proposed studies. The self-adhesive surface electrodes used to record surface EMG may produce minor irritation (redness, itching) of the skin under the electrodes. There are minimum risks associated with needle EMG. Subject may feel irritation, discomfort and pain during needle insertion. Needle insertion may also associate with bleeding. Bleeding is minimum should it occur. Electrical stimulation may cause an unusual sensation that can be painful at higher intensities. Note that risks associated with botulinum toxin injections will be addressed by treating physicians clinically, not in the scope of this research project. Post-Botox injection pain with 3DIZI guidance or conventional guidance is rare. It is common clinical practice that patients are advised to take over the counter pain killer for such pain if it does occur.

8. Benefits:

The benefit of this research will be the contribution it makes to knowledge, particularly our understanding of motor unit 3D localization within the spastic-paretic muscles, and development of possible guidance for botulinum toxin injection. Stroke subjects who receive 3D IZ guided injection may benefit from the research project in that the effect of injection may be maximized.

9. Risk-benefit Ratio:

In view of the minimal risk, the knowledge to be gained far outweighs the risks.

10. Consent Procedures:

Informed consent will be obtained from the subject. After the subject is identified and is interested in participating, informed, written consent will be obtained by the investigator.

11. Confidentiality Procedures:

In order to minimize risk to confidentiality, all data will be de-identified, coded with a study-specific identification number, maintained on a password-protected server, and/or kept in a locked office. No findings will be released without written authorization by the subject or requests by law.

12. Costs:

The subject will not be expected to pay any costs. Routine BoNT injections are part of their standard of care

13. Payments:

There will be no costs to subjects. Instead, subjects will receive a gift card of \$40 for their participation in Experiment 1. They will receive gift cards in a total amount of \$80 after last visit (a total of 3 visits) in Exp 2.

14. References:

- Bakheit, A. M. O. (2006) The possible adverse effects of intramuscular botulinum toxin injections and their management. *Current drug safety* 1,271-279

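### Injection-related events are declared outside the research although the study method sets needle site and depth in one group, so none enters the study data by group

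*Combined protocol and SAP*

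**What the plan says.** Section 7 (Potential Risks/Discomforts) describes the risks of surface electrodes, needle EMG and electrical stimulation. It then states that "risks associated with botulinum toxin injections will be addressed by treating physicians clinically, not in the scope of this research project". It adds that pain after injection is rare with either type of guidance, but cites no data for the guided method.

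Section 4, Experiment 2 (BTX injections), says of the guided group: "The surface location and depth information of the IZ will be used to guide where the needle tip needs to go". The mapping "will be applied to the IZ-guided injection group 1 day prior to scheduled injection", so it is done in one group only. The study also fixes the number of sites in both groups: "To standardize the procedure, we will choose 2 sites for all patients". On product quantity, the "amount of BTX (usually 100 units) and dilutions (usually double dilution) will be consistent between two groups".

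Section 3 (Innovation of this project) says of the technique: "Moreover, it is also expected to minimize possible adverse effects". The background in the same section states: "The occurrence and severity of side effects are dependent on the delivered dose of toxin". It also reports that the method has been validated in the biceps of 2 healthy men but not in spastic muscle.

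For outcomes, Section 4 says: "Treatment outcomes include clinical assessment of spasticity (MAS scale, see Human Subject Protection section) and quantitative assessment". The quantitative assessment is reflex torque. Section 6 plans a two-way ANOVA on reflex torque and a descriptive analysis of demographic data. Neither section mentions adverse events.

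**The concern.** Section 7 treats injection risk as part of routine care. That fits the type, dose and dilution of toxin, which the protocol describes as standard at the clinic. It does not fit needle placement in the guided group, where site and depth come from the technique under study. Placement is the intended difference between the groups, yet its possible harms are put outside the research.

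At stake is basic tolerability information from a feasibility study. Section 4 says the results will inform whether a future study needs more subjects. If guided placement caused a common problem, such as more local reactions or more unwanted weakness, the study data set would hold nothing by group that showed it.

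**Working it through.** The plan gives no adverse-event figure to reproduce. Its one related design figure is 8 patients per group in Experiment 2. That cannot be reproduced either, because the protocol states no alpha, power, effect size or standard deviation. The check therefore has two parts: the text, and what 8 per group could show.

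**Text, side by side**

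1. *Scope.* Section 7 places injection risks outside the research and gives them to the treating physicians.
2. *Who decides placement.* Section 4 lets the research mapping decide site and depth in the guided group. In the standard group, ultrasound confirms that the needle tip is in the muscle.
3. *What is collected.* Sections 4 and 6 name MAS and reflex torque at baseline, 3 weeks and 3 months. No section provides for collecting, attributing or tabulating adverse events, or for a route from the clinic record to the study data.
4. *What the safety expectation rests on.* Section 3 ties side effects to dose and expects the technique to permit a lower dose. Experiment 2 holds dose consistent between groups, so a benefit through lower dose cannot appear. Any difference in events would reflect placement at equal dose, plus chance and any imbalance between groups.

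Items 1 to 3 together mean that, as written, injection-related events are not study data in either group.

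**What recording by group could show (n = 8 per group)**

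- Upper limit on the true rate after 0 events in 8:
  - one-sided 95%: 1 − 0.05^(1/8) = 0.312, about 31%;
  - two-sided 95% (exact): 1 − 0.025^(1/8) = 0.369, about 37%.
- Chance of at least one event in a group, 1 − (1 − p)^8. The rates p are assumptions, as the protocol gives none:

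| Assumed true rate p | Chance of ≥1 event in 8 |
|---|---|
| 5% | 0.34 |
| 10% | 0.57 |
| 20% | 0.83 |
| 30% | 0.94 |

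- Formal comparison by Fisher's exact test, two-sided: 4/8 against 0/8 gives p = 0.077, and 5/8 against 0/8 gives p = 0.026. When one group has no events, the other needs at least 5 of 8 for p below 0.05. At assumed rates of 10% and 30%, power is about 3%; at 10% and 50%, about 22%.

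Systematic questions would therefore probably bring at least one case of a common problem to light. They could neither establish safety nor support a test between groups.

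**The case against.** The strongest reply is that Section 7 assigns clinical responsibility and does not forbid recording. A reader might infer an explicit rule against collecting events; the sentence does not say that. This part of the reply stands. The gap comes from the scope clause together with outcome and analysis sections that list no events.

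A reader might also infer that the trial would leave no information on the safety of guided placement. The documents do not support that. Participants are clinic patients on repeated injections, and their physicians continue to observe them. What is missing is a stated route from that observation into comparable data by group.

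A third tempting reading is that the plan makes a safety claim which event recording would test. The expectation stands under Innovation, is linked largely to dose reduction and is not an Experiment 2 hypothesis. With equal dose, counts by group would neither confirm nor refute it by that route.

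Other limits also stand:

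- Both groups receive the same product, dose, dilution and number of sites, and the imaging is confined to the biceps.
- Experiment 1 is designed to validate the method in spastic biceps, although the protocol does not make Experiment 2 wait for its result.
- Section 4 allows other elbow flexors to be injected, not necessarily consistently across patients, so weakness or spread would be hard to attribute to the biceps injection.
- The consent pages are not in the public text and may describe event reporting.

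None of this removes the mismatch between the scope clause and the study's own control of needle placement.

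**Conclusion.** The point holds in a limited form. The protocol puts injection risks outside the research while its own method sets site and depth in one of the two groups, and it lists no outcome that would bring injection-related events into the study data by group. This is a cheap improvement and does not undermine the reflex-torque comparison.

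The yield is modest. Even a clean record of 0/8 would leave true rates up to about 31% (one-sided 95%) or 37% (two-sided 95%) unexcluded. These limits assume that all 8 patients in the group are followed and asked; with fewer they would be wider. The conclusion also assumes that no event collection by group is described in pages outside the public text.

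**What to change.** 1. In Section 7, keep the text that leaves clinical handling of injection risks to the treating physicians. Amend only the scope clause, so that injection-related events in Experiment 2 are recorded as study data.
2. In Section 4, add the same short set of adverse-event questions for both groups at the existing 3-week and 3-month visits. Local reactions, excess weakness, spread to nearby muscles and any other event would be a reasonable list; the exact items are for the investigators.
3. Record for each patient which other elbow flexors were injected, so that weakness or spread can be read with that in view.
4. In Section 6, plan one table of counts by group, descriptive and without a test. State there that 0/8 would exclude only rates above about 31% (one-sided 95%) or 37% (two-sided 95%), that the data cannot establish safety, and that equal dose means they say nothing about a benefit from dose reduction.

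The cost is a few minutes at each of two visits that already take place, and one table. No visit, procedure or patient is added. Someone must be named to ask the questions, since the protocol lists the study coordinator as not yet identified.
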